### **Recruitment:**

Participants are recruited by placing flyers around the community that ask for responses from “heavy smokers who are interested in research and are between the ages of 18-50 years”. Participants are also recruited via Craigslist using a post titled “Participants Needed for Psychology Study.” After calling or emailing the lab, interested participants complete a 5 minute phone screen to determine eligibility (e.g., smoking at least 15 cigarettes per day). These phone screens will be de-identified and retained to show eligibility to participate. Once in the laboratory participants also complete the nicotine dependence severity scale to quantify the severity of their nicotine dependence. [name] and Brown have successfully recruited populations of heavy smokers for fMRI studies in the past. Subjects who express interest by calling or emailing the lab will be contacted via telephone by the lab subject coordinator. They will be asked a series of screening questions to confirm that they meet the inclusion/exclusion requirements. This screening interview will be oral and no information will be recorded or retained, as it is for screening purposes only. If subjects meet the inclusion criteria, they will then be asked to provide a schedule of availability and placed on a list of interested subjects. They will be informed that they may or may not be offered a spot in our current study, depending on available timeslots and how many participants we will run in relation to how many interested respondents we have. As volunteers are needed for specific time slots, the research coordinator will contact them to schedule them, and the first subject that is available for the required session time will be scheduled. Interested participants who meet all screening criteria but who are not offered a slot in our current study will be informed that they have the option to be put on our contact list for future studies. Previously interested volunteers will be removed from the contact list immediately if they so request.

[figure not shown]

## Safety – Electrical Neurostimulation

Temporal interference tACS has been used since at least the 1970s in humans and safely at current levels over 10 times what we propose here (Venancio et al., 2013).

Grossman et al. (2017) determined the safety of TI by comparing the brain tissue of stimulated and unstimulated mice at currents of 125 mA per electrode pair (F1 = 2 kHz, F2 = 2.01 kHz) were applied in a 10 seconds-on, 10 seconds-off pattern for 20 min. Results showed no evidence of tissue damage. Notably, they found no tissue damage even when their tested stimulation of 125 mA was substantially larger than that applied normally in humans or will be applied in the proposed work. Grossman et al. (2017) found no differences in neuronal density, number of apoptotic cells, reactive microglia/astrocytes, or synaptic density, and no presence of DNA damage following stimulation vs. control. The current study proposes oscillatory frequencies of F1 = 2 kHz and F2 = 2.01 kHz, creating an envelope frequency of 10 Hz, with each current not exceeding a peak-to-peak amplitude of 2 mA. F2 may be varied up to 2.1 kHz to investigate the effects of different envelope frequencies. This creates a total of 4mA of alternating currents.

This alternating current amplitude was chosen based on recent findings that between 4-6 mA is required to reliably and efficaciously impact neural circuits, as  $58 \pm 7\%$  of alternating current is blunted by skin and tissue and  $16 \pm 8\%$  is attenuated by the skull (Vöröslakos et al., 2017). Other research has indicated that even 4 mA of direct current stimulation for 30 minutes has been safely tolerated (Bikson et al. 2016; Nitsche & Bikson, 2017). For transcranial alternating current stimulation as used by TI, there is also a question of what current frequencies can be safely applied. Chaieb et al. (2014, <https://doi.org/10.1016/j.brs.2013.08.004>) show that transcranial alternating current stimulation at a frequency up to 5KHz with a current of 1 mA for 10 minutes is safe, with no evidence of increased neuron specific enolase, a marker of neural injury. A recent review of adverse events of tACS and tDCS shows no serious adverse events. The potential minor side effects of tDCS include skin irritations, and no adverse effects of tACS have been reported (Matsumoto and Ugawa, 2017, <https://doi.org/10.1016/j.cnp.2016.12.003>). Stimulation with tACS at 2mA with frequencies of 10, 50, and 300 Hz for 5 minutes has been done with no adverse effects (Naro et al., 2016, <https://doi.org/10.1016/j.brs.2016.02.005>). Given these prior findings of safety for the types of stimulation we plan to administer, we do not expect adverse events beyond minor skin irritations in the rare case. There is some evidence that electrical neurostimulation may lead to effects that persist beyond 6 months. One study found that tDCS stimulation during learning may lead to lasting improvements in numerical abilities 6 months after training (Cohen Kadosh et al., 2010).

## Safety – TI-NDBS device

The TI-NDBS device has the following safety features, designed to prevent malfunction and, if a malfunction were to occur, automatically reduce the electrical current to prevent injury to the patient:

- 1) **Intrinsic limits:** It has a 9 volt power supply, which limits the electrical stimulation power that can be delivered.
- 2) **Safety monitoring circuit:** It has a built in voltage monitor to detect malfunctions and take corrective action. The device is designed to deliver a fixed amount of current, up to 2 mA per channel. The voltage is constantly adjusted to compensate for the electrical resistance of the

head and maintain the desired electrical current. If the resistance increases such that the voltage reaches the maximum possible device voltage (e.g. due to a poor connection with the scalp), then the device will signal an error via an LED light and lower the set point current to avoid excessive voltage. In plain language, the device has a built-in monitor that will immediately detect malfunction and reduce the current.

### **MR safety of TI-NDBS device**

Our MR physicist, [name], assesses that the stimulator will be safe for the MR scanner, provided:

- 1) the stimulator circuit remains in the control room, and
- 2) the wires do not form loops, but go straight down the bore of the scanner, and
- 3) there are inductive RF filters along each wire, to filter out RF noise

Furthermore, prior to human subjects tests, we will test the MR safety of the stimulator by hooking it up to a phantom load (e.g., a piece of meat), running the stimulator while the scanner is running an fMRI sequence, and checking the actual current delivered (via an oscilloscope) to verify that the signal does not suffer from interference or produce overcurrent due to magnetic and/or RF interference.

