**Phase 2. Neural effects.** In Phase II, subjects will complete the MRI safety screen questionnaire and the stimulation experience scale (the same scale from phase 1) prior to entering the MR scanner. The electrodes (2 cm x 2 cm) will be attached and subjects will enter the MR scanner and the TI-NDBS stimulation will be administered while in the scanner, alternating 2-minute stimulation and 2-minute no-stimulation periods. Subjects may alternatively receive stimulation from all electrodes at the same frequency in order to make comparisons to temporal interference stimulation. For every two minute period of stimulation, the current will increase slowly at a constant rate for 30 seconds until it reaches the appropriate intensity. At the end of the stimulation, the current will decrease slowly for 30 seconds until it reaches zero. For sham stimulation, the current will increase during a 30 second interval and then immediately decrease back to zero over a 30 second interval, for a total of 60 seconds of stimulation. This will allow us to identify immediate neural activation due to stimulation, while controlling for any scalp sensations with the sham condition. The electrodes will be placed to target stimulation at either anterior Cingulate or nucleus accumbens. Immediately following the stimulation session, subjects will complete the stimulation experience scale and then will clean off residual electrode gel. The stimulation experience scale is administered again 30 minutes later. The subject will be in the scanner for about 1 hour.

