## **6.0 Statistical Analysis and Sample Size:**

In phase 1, we will assess tolerability with an initial cohort of 3 stimulation subjects. Our aim here is to identify any potential adverse effects, using two approaches. We will monitor the stimulation condition for clinically significant adverse effects such as seizures, prohibitive pain, etc, though we do not expect this based on all the literature from earlier studies.

In phase 2, we will conduct a pilot assessment to determine whether and how the stimulation immediately influences neural activity. As this is a within-subjects pilot design intended to estimate the effect size of neural activation, we will scan 10 subjects, comparing the neural activation in each subject during the stimulation period with neural activation in the same subject during the no-stimulation periods. We do not have a power analysis for this phase yet, because the whole point is to perform a pilot study in order to estimate the effect sizes. We anticipate that 10 subjects will be sufficient to estimate the effect sizes.

In phase 3, we will proceed in two parts. During the first pilot part, we will recruit 5 subjects in each of 3 groups, to identify which two of the three candidate brain regions seem most promising sites of stimulation to reduce nicotine craving and consumption. Once we identify the two more promising sites of stimulation, we will proceed to the second part. We do not have a power analysis for this part because again, we are looking to estimate the relative effect sizes for one stimulation site compared to another. For the second part, we will recruit 45 subjects who are heavy smokers into three groups of 15 each, then ask them to abstain from smoking for several hours prior to the session. The first group will receive TI-NDBS over the most promising site. The second group will receive TI-NDBS over the second most promising site. The third group will receive sham stimulation. We will measure total real-time ad lib nicotine vapor inhalation during a 60 minute stimulation session, and every ten minutes, we will ask subjects to

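### The pre-study phantom scan checks the stimulator current but not the images, so the Phase 2 on/off contrast could not tell a current-locked image artefact from a neural effect.

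*Combined protocol and SAP*

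**What the plan says.** Section 3.0, under MR safety of TI-NDBS device, sets out one bench test: "we will test the MR safety of the stimulator by hooking it up to a phantom load" while an fMRI sequence runs, and "checking the actual current delivered (via an oscilloscope) to verify that the signal does not suffer from interference". The read-out is the delivered current, and the signal checked for interference is the stimulator's own. The only filtering safeguard is given there as a condition of MR safety: "there are inductive RF filters along each wire, to filter out RF noise".

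The Phase 2 part of section 3.0 specifies "alternating 2-minute stimulation and 2-minute no-stimulation periods". On the ramps it says: "For every two minute period of stimulation, the current will increase slowly at a constant rate for 30 seconds until it reaches the appropriate intensity". A 30 s ramp down ends each period. Sham ramps up for 30 s and straight back down, "for a total of 60 seconds of stimulation", and its stated purpose is "while controlling for any scalp sensations with the sham condition".

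Driving all electrodes at one frequency, for comparison with TI, is described in two places. The Phase 2 text offers it as something subjects may receive instead. The New technology text says subjects will also receive it.

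Section 5.0 sets the Phase 2 endpoint as activity under TI-NDBS against no stimulation. Section 6.0 analyses 10 subjects by "comparing the neural activation in each subject during the stimulation period with neural activation in the same subject during the no-stimulation periods". Neither section mentions sham or same-frequency stimulation for Phase 2.

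**The concern.** Phase 2 exists to estimate the size of the neural response to stimulation. Its written analysis compares images taken with current in the head leads against images taken without. Any change that the current itself makes to the images appears and disappears on the same timetable. The on/off contrast has no means of dividing that change from a blood-flow response.

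The planned phantom run is the natural place to look for such a change, because a piece of meat has no neural response. As written, it looks in one direction only, from scanner to stimulator. The device is custom-built, and the documents report no image-quality record for it. At stake are the Phase 2 effect size and the localisation that section 2.0 assigns to this phase.

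**Working it through.** The plan gives no power, effect size, SD, alpha or named test for Phase 2, so there is no stated figure to reproduce. The steps below show how closely an artefact would follow the contrast, what the available controls would remove, and what a given artefact would do to a test.

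**Inputs from the documents.** 120 s on and 120 s off; 30 s ramps up and down; sham of 30 s up and 30 s down; n = 10, within subject.

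**Assumptions.** The ramps lie inside the 120 s period. Sham occupies one 120 s period. The artefact is proportional to the current. The test is a paired t-test at two-sided 5%.

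**1. Alignment.** Let A be the current as a fraction of peak and B the on/off indicator, over one 240 s cycle.
- Mean of A in the on period: (30 × 0.5 + 60 × 1 + 30 × 0.5)/120 = 0.75. Over the cycle it is 0.375, and the mean of B is 0.5.
- Mean of AB over the cycle: 0.375. Covariance: 0.375 − 0.375 × 0.5 = 0.1875.
- Mean of A² in the on period: (60 × 1/3 + 60 × 1)/120 = 0.667. Over the cycle it is 0.333. Variance of A: 0.333 − 0.375² = 0.1927.
- Variance of B: 0.25.
- Correlation: 0.1875/√(0.1927 × 0.25) = 0.854.

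Against a regressor that includes the ramps and is convolved with a haemodynamic response, the correlation was computed as 0.99.

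**2. What the controls would remove.**
- Sham: its mean current over 120 s is (30 × 0.5 + 30 × 0.5)/120 = 0.25 of peak, against 0.75 for active. Active minus sham keeps (0.75 − 0.25)/0.75 = two thirds of the artefact.
- Same-frequency stimulation with equal current and timing would carry nearly the same artefact without the beat. TI minus same-frequency would largely cancel it.

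**3. Effect on a test.** Suppose the neural effect is zero and the artefact shifts the mean on-minus-off difference by b between-subject SDs. Then t has a noncentral t distribution with 9 degrees of freedom and noncentrality b√10, and the critical value is 2.262.

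| b (assumed) | b√10 | Rejection rate |
|---|---|---|
| 0 | 0 | 5% |
| 0.25 | 0.79 | 11% |
| 0.33 | 1.04 | 15% |
| 0.5 | 1.58 | 29% |
| 0.75 | 2.37 | 56% |
| 1.0 | 3.16 | 80% |

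The rate is the same for an artefact of either sign. A negative artefact would pull the estimate down rather than up.

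**The case against.** The best defence is that the design already contains the control it needs. Same-frequency stimulation at matched current would separate TI from artefact, and sham would help. This stands as a description of what could be done. It does not stand as a description of what is planned: the condition is optional in one part of section 3.0, planned in another, and absent from sections 5.0 and 6.0. Sham is there for scalp sensation and cancels only about a third.

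It is also fair that no document shows an artefact. The stimulator circuit stays in the control room, the wires run straight, each has an RF filter, and the current is sinusoidal with no DC component. These measures may be enough, but no step verifies that for the images. Testing the current in a safety section is not itself a mistake.

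Three stronger readings are tempting and not supported.
- **That an artefact would coincide perfectly with the contrast and could not be separated.** The ramps and the same-frequency condition both argue against this.
- **That later phases rest on the Phase 2 effect size.** Phase 3 pilots all three regions regardless and selects on craving and consumption. The Phase 4 site comes from Phase 3. Electrode placement is set by finite element modelling.
- **That the slow 240 s cycle would be filtered away.** The plan states no high-pass cut-off. If data and model are filtered alike, a short cut-off costs precision and does not bias the estimate. The analyst need only choose a cut-off longer than 240 s.

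**Conclusion.** The point holds as a gap in verification. The plan tests whether the scanner disturbs the current and never tests the reverse. Its only written Phase 2 contrast could not tell a current-locked image change from a neural response. The alignment is close: about 0.85 with a plain on/off pattern and 0.99 with a ramped, convolved regressor.

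The rejection rates of 15%, 29% and 80% are illustrations. They rest on assumed artefact sizes of 0.33, 0.5 and 1.0 SD and on an assumed paired t-test. The documents give no figure for either, so a reader should not infer that Phase 2 is contaminated or that any of these rates is expected. The consequence is confined to the interpretation of Phase 2, its effect size and its localisation. It is worth correcting because the phantom scan is already planned, and because an artefact could not be reliably ruled out from the on/off contrast once the ten subjects have been scanned.

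**What to change.** **Section 3.0, MR safety of TI-NDBS device.** Run the planned phantom scan with the Phase 2 leads, filters, sequence and on/off timing, and keep the images. Apply the Phase 2 on/off analysis across the phantom volume and compare temporal signal-to-noise with the stimulator on and off. Set the acceptance limit beforehand, and meet it before Phase 2 scanning begins. The check should cover the whole volume, since a piece of meat has no target regions.

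**Sections 5.0 and 6.0.** Name TI versus same-frequency stimulation, at equal current and timing, as a Phase 2 contrast alongside on versus off. State what the sham comparison is meant to show.

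**Section 3.0, Phase 2 and New technology.** Reconcile the two statements on whether subjects may or will receive same-frequency stimulation. The added contrast is available only in subjects who do.

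**Cost.** A somewhat longer phantom run and one extra analysis, plus scanner time for same-frequency periods where these were not already intended. A clean phantom lowers the concern but does not remove it, because it cannot reproduce motion or physiology in people. That is why the added contrast is needed as well.

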### **TI device**

The TI device was custom-built by the machine shop in the department of Psychological and Brain Sciences based off of schematics that [name] (PI) and [name] (Ph.D., electrical engineer) devised based on the work of Grossman et al. 2017 (for device images and circuitboard diagram see the Notes & Attachments). The TI device contains a mechanism that constantly monitors the amount of current administered via the electrodes. The current study design is single-blind such that the experimenter will become aware of the amount of current administered to ensure the safety of experimental subjects. A prototype of the device is shown in Figure 2. The device has the following characteristics:

- The device is powered by standard 9-volt batteries that provides the energy to carry out the neurostimulation. The device may also be powered by a standard 9-volt power supply.
- There are two electrode pairs, with a total of 4 electrodes, that will connect from the device in Figure 2 to gel electrodes on the subject's head (as shown in Figure 1), typically of varying shapes approximately 2 cm x 2 cm. At 2 mA current, this will result in a maximum current density of  $0.0005 \text{ A/cm}^2$ . At 50Kohm scalp impedance, the total power dissipated by an electrode pair is  $I^2R = 200 \text{ mW}$ , which is comparable to the power emitted by a cell phone.
- Each electrode pair generates a sinewave alternating current, with no DC component. The frequency can be varied continuously from zero to over 5 Khz. We will not apply alternating current frequencies over 5Khz. Typically, the frequencies will be around 2 Khz.

- The frequency difference between the electrodes will be varied between 1-100 Hz.
- The current for each electrode pair can be controlled continuously from zero to 2 mA. Each of the two electrode pairs may have a different current level, which allows the focal point of stimulation in the brain to be steered without moving the electrodes.
- For safety, the device includes an onboard current monitor to measure the amount of current actually delivered. The device can be powered down if for any reason the amount of current exceeds the specified setting, or if the voltage required to deliver the current exceeds the device's capacity.
- The device settings are controlled by a separate microcontroller, typically a Raspberry Pi zero, which communicates with the device via serial protocols, namely SPI and I2C. The raspberry pi is a fully functional computer that can be programmed to run timed stimulation protocols and control the neurostimulator.
- The four electrodes will be placed on the subject's scalp (Figure 1) at locations designated in the international 10/20 system, as used for EEG. The locations will be optimized by finite element modeling to target specific brain regions such as the dorsal anterior cingulate cortex (dACC), insular cortex, and nucleus accumbens.
- Should stimulation be terminated early for any reason, the same stimulation assessments will be conducted as if the session lasted the full 40 minutes including the EMA, stimulation experience scale, heart rate, blood pressure, psychiatric symptoms, nicotine craving, etc. The reason for termination will be recorded and an unanticipated event filed with the IRB. If the subject experiences an adverse reaction to the stimulation, this will be recorded and reported to the IRB and DSMB.

